**The current status and progression of
symptoms and comorbidities among
male lower urinary tract symptoms
patients in China: a multicenter study
from Prostatic Obstruction
Investigation Team (POInT)**

December 19, 2017

Title

The current status and progression of symptoms and comorbidities among male lower urinary tract symptoms patients in China: a multicenter study from Prostatic Obstruction Investigation Team (POInT).

Aims

Aim one: To investigate the symptom features and comorbidities among male lower urinary tract symptoms patients in China.

Aim two: To determine the progression of lower urinary tract symptoms and comorbidities after medication or surgical treatment during prospective follow-ups.

Inclusion Criteria

[figure not shown]
1. Male, 45 years or older.
2. The presence of lower urinary tract symptoms, i.e. frequency, urgency, urge incontinence, dysuria, post-micturition dribble, etc.
3. All participants have signed the informed consent form.
4. Clinical data comes from 23 selected hospitals spread across China.

Exclusion Criteria

[figure not shown]
1. Lower urinary tract symptoms as a result of urethral stricture, stone diseases, chronic prostatitis, space-occupying lesions etc.
2. Diagnosis or suspicion of renal, ureteral, bladder, prostate, urethral or pelvic tumor.
3. Known neurogenic or congenital lower urinary tract dysfunction.
4. Known urinary tract, prostate or pelvic surgical history.
5. Existence of anatomical abnormalities of the urinary tract (e.g. diverticulum of the bladder or urethra, ectopic ureteral orifice etc.).
6. The presence of acute conditions, such as, urinary tract infection, fever, heart failure etc.
7. Patients with poor compliance or cognitive competence.

Study design flow diagram

[figure not shown]
Overall design

Stage I

Stage II

Statistical Analysis

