The statistical analysis will be performed using sas software version 9.4 or higher. Quantitative data will be presented as mean \pm standard deviation; Categorical and ranked data will be presented using frequency and proportion. Normal distributed and equal variance quantitative data will be analyzed using independent sample t test, otherwise using a Wilcoxon rank sum test. Categorical data will be assessed by Chi-square test and Fisher's exact test. Ranked data will be analyzed by Wilcoxon rank sum test. Multivariate analysis logistic regression will be used to screen risk factors in the binary variables. The level of significance will be established at <0.05 .

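### Normal data with unequal variances go to the rank sum test; read as a test of the reported means, its level can leave 0.05 when group sizes differ

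*Combined protocol and SAP*

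**What the plan says.** The Statistical Analysis section sets one general rule for comparing quantitative data between two groups: "Normal distributed and equal variance quantitative data will be analyzed using independent sample t test, otherwise using a Wilcoxon rank sum test". The t test needs both conditions, normality and equal variance. Everything else goes to rank sum, including data that are normal but differ in variance. No unequal-variance (Welch or Satterthwaite) t test is named, and neither are the tests that would decide normality or equality of variance.

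The same section says "Quantitative data will be presented as mean" with standard deviation. It gives no other summary for variables that end up in the rank sum branch. Ordinal data have their own rule: "Ranked data will be analyzed by Wilcoxon rank sum test". On the level: "The level of significance will be established at <0.05". No null hypothesis is stated for any test.

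Under Aims, the second aim is: "To determine the progression of lower urinary tract symptoms and comorbidities after medication or surgical treatment during prospective follow-ups". The readable text does not say that medication and surgery patients will be compared with each other, and it fixes no ratio between them.

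**The concern.** In this branch the data have been judged normal, so the mean is a natural target and a standard test of means exists. The plan uses rank sum instead and prints means and SDs beside its p value. A reader will tend to take that p value as a test of the difference in means.

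The rank sum statistic is standardised with a variance that holds when the two distributions are identical. If the means are equal but the SDs differ, the true variance is different. The error depends on which group is more variable:

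- **Smaller group more variable:** the test rejects equal means too often.
- **Larger group more variable:** it rejects too rarely and loses power.

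At stake is the meaning of 0.05 for any quantitative comparison that falls into this branch. Medication and surgery groups, if compared, could well differ in size, but the readable text does not establish that.

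**Working it through.** **Inputs.** From the plan: the test rule, mean and SD as the summary, and a level of 0.05 (two-sided assumed, critical value 1.96). Group sizes and SDs are not given, so every scenario below is an assumption: normal data, equal means, 400 patients in total, SD ratio r of 1.2, 1.5, 2 or 3. The plan has no figure of its own to reproduce.

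**Formula.** Let m be the size of the group with the smaller SD, n the size of the other, and λ = m/(m+n). For equal-mean normal data define

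- v1 = asin[(1/r²)/(1 + 1/r²)] / 2π
- v2 = asin[r²/(1 + r²)] / 2π

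The large-sample variance of the scaled Mann-Whitney statistic is V = v1/λ + v2/(1−λ). The test assumes V0 = (1/12)[1/λ + 1/(1−λ)]. Its actual level is 2[1 − Φ(1.96·√(V0/V))].

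**Worked case: SD ratio 2, sizes 300 and 100.** v1 = asin(0.2)/2π = 0.0320; v2 = asin(0.8)/2π = 0.1476; V0 = (1/12)(1/0.75 + 1/0.25) = 0.4444.

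- Smaller group more variable (λ = 0.75): V = 0.0320/0.75 + 0.1476/0.25 = 0.633. The effective critical value is 1.96·√(0.4444/0.633) = 1.64, so the level is about 10%.
- Larger group more variable (λ = 0.25): V = 0.0320/0.25 + 0.1476/0.75 = 0.325. The effective critical value is 1.96·√(0.4444/0.325) = 2.29, so the level is 2.2%.

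**Rank sum level (%), read as a test of equal means**

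| Sizes | More variable group | r = 1.2 | 1.5 | 2 | 3 |
|---|---|---|---|---|---|
| 300 vs 100 | smaller | 6.2 | 7.9 | 10.0 | 12.7 |
| 267 vs 133 | smaller | 5.8 | 7.0 | 8.7 | 10.8 |
| 240 vs 160 | smaller | 5.5 | 6.3 | 7.5 | 9.3 |
| 200 vs 200 | either | 5.1 | 5.3 | 5.9 | 6.9 |
| 240 vs 160 | larger | 4.6 | 4.4 | 4.3 | 4.7 |
| 267 vs 133 | larger | 4.3 | 3.7 | 3.3 | 3.2 |
| 300 vs 100 | larger | 4.0 | 3.0 | 2.2 | 1.7 |

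The table uses the finite-sample variance, which agrees with the formula above to within 0.03 points. Simulation at 300 vs 100 (40,000 datasets per cell) gave 6.4 / 7.8 / 9.9 / 12.7% and 3.8 / 2.9 / 2.1 / 1.8%. Welch without pre-testing, simulated in all these cells, gave 4.8 to 5.2%.

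**Power.** At 300 vs 100 with the larger group more variable and Welch at about 80%, rank sum had about 75 / 71 / 66 / 58% at the four SD ratios.

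**The decision rule as a whole.** The plan names no pre-tests, so Shapiro-Wilk and Levene at 5% were assumed. Levels (%) at 300 vs 100 with the smaller group more variable, 10,000 datasets per cell:

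| Rule | r = 1.2 | 1.5 | 2 | 3 |
|---|---|---|---|---|
| As written | 6.6 | 7.9 | 9.7 | 12.8 |
| Only the normal, unequal-variance branch changed to Welch | 6.1 | 5.5 | 5.7 | 6.2 |
| Variance pre-test dropped, normality pre-test kept | 5.6 | 5.5 | 5.7 | 6.2 |
| Welch, no pre-test | 5.3 | 5.0 | 5.1 | 5.1 |

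What remains in the two middle rows arises mainly because about 10% of truly normal datasets fail the normality pre-test and still go to rank sum.

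**The case against.** The strongest reply is that the plan contains no error as written. Rank sum holds 5% for its own null, and the plan never says it tests means. Reporting mean and SD is a blanket descriptive rule and does not define what the test compares. Four things must coincide for harm: a normal variable, unequal variances, unequal group sizes and a reading in terms of means. The readable text names no quantitative variable, group size or two-group comparison. The flow diagram is not reproduced, and the Overall design, Stage I and Stage II headings carry no text, so such details may exist there. The large figures need large imbalances: at 240 vs 160 with SD ratios of 1.2 to 1.5 the level is 4.4 to 6.3%. At 300 vs 100 with ratio 1.2 and the smaller group more variable, changing only the one branch moves the level just from 6.6% to 6.1%.

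Most of this stands as a limit on importance. It also has to be granted that rank sum departs less than the pooled t test would: in simulation at 300 vs 100, ratio 2, smaller group more variable, pooled t gave 15.0% and rank sum 10.0%.

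It does not remove the point. In this branch the variances have already been judged unequal, so a null of identical distributions has been set aside before the test is run. What remains of interest is the difference in location, and the means are what the reader will see. A test that holds its level for that question is available at almost no cost.

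**Conclusion.** The point holds as a conditional one. The rule sends normal, unequal-variance data to a test whose level, read as a comparison of means, ranged from 1.7% to 12.7% over the assumed scenarios (size ratios up to 3:1, SD ratios up to 3). With equal groups and an SD ratio of at most 2 it stayed between 5.1% and 5.9%. The actual departure in this study cannot be fixed, because the readable text gives neither sizes nor SDs.

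No confirmatory comparison depends on this rule, so the point is a refinement worth considering. It does not undermine a main conclusion.

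**What to change.** **Preferred.** For variables treated as approximately normal where means are compared, use the Welch (Satterthwaite) t test for all of them, without a variance pre-test. Preferably list those variables in advance, so that no normality test on the same data chooses the method. Keep rank sum for ranked or markedly skewed variables, interpret it as a difference in distributions, and report median and quartiles beside its p value.

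**Minimal.** If the pre-test branching stays, change only the normal, unequal-variance branch to Welch. The level is then near 5% but not exactly 5%, as shown by the second row of the decision-rule table.

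**Cost.** One sentence in the Statistical Analysis section, plus the variable list if it is adopted. Power lost when variances are equal is negligible: at 300 vs 100, 79.4% for Welch against 79.9% for pooled t.

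The real downside is skew. With equal means and the smaller group more variable, simulated Welch levels were:

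| Distribution | 300 vs 100 | 270 vs 30 |
|---|---|---|
| Gamma, SD 0.5 vs 1.5 | 6.6% | 8.9% |
| Lognormal, log-SD 0.5 vs 1.0 | 7.6% | 11.4% |

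Welch should therefore not replace rank sum for markedly skewed data.
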